4.2 SCIENTIFIC RATIONALE FOR STUDY DESIGN

To determine whether to test sirolimus in a large phase 3 trial, we propose to conduct a clinical trial of sirolimus in MSA using a futility design. This approach minimizes the number of subjects and resources required for the study and provides an indication of whether or not to pursue larger and more definite studies. A futility design (60) is highly appropriate for MSA given: a) the low prevalence of the disease; b) the availability of historical controls from recent large studies (8, 39); and c) the availability of sensitive outcome measures. A futility design under the null hypothesis assumes that sirolimus will slow the progression of the disease, whereas the alternative hypothesis assumes no benefit of sirolimus. If the null hypothesis is rejected (i.e., futility of sirolimus to slow progression of MSA), a major phase III study will be discouraged, whereas non-futility will offer strong support for a phase III trial to detect clinical efficacy.

This study will also include a placebo group in 3:1 proportion. Our reason for including a placebo arm is to facilitate blinding to treatment assignment and also to permit a descriptive assessment of the validity of the assumed change in UMSARS over time in the historical control group; it will not be used as a basis of comparison for the active treatment arm.

This placebo-controlled futility design comparing outcome measures to historical controls has been used in other neurodegenerative disorders (61-63).

The study population (n=42 active agent, n=14 placebo) was selected based on power analysis calculation using the known annual progression of the UMSARS total score from published natural history studies (8, 39) and the progression in the placebo group of previous clinical trials of MSA(40), as well as from the minimally clinically significant difference in UMSARS (38) (see statistical section).

4.3 JUSTIFICATION FOR DOSE

We will use sirolimus dosages of 2 mg, 4 mg or 6 mg, once a day based on therapeutic drug monitoring in order to maintain sirolimus drug levels within a FDA-recommended target-range: 5-20 ng/ml. This daily dosage is within the range that is used clinically, and we expect this dose to be well tolerated. This is well below the currently FDA-approved maximum sirolimus dose administered per day, which is 40 mg (54). The use of sirolimus for 1 year is known to be safe, based on long experience in the prevention of organ transplant rejection, without significant complications (64, 65). Moreover, there is ample evidence that sirolimus at these dosages crosses the blood-brain barrier (31-35).

4.4 END OF STUDY DEFINITION

A participant is considered to have completed the study if he or she has completed all phases of the study including the last visit or the last scheduled procedure shown in the Schedule of Activities (SoA), Section 1.3.

The end of the study occurs when the following circumstance have ALL occurred:

1. Completion of the last visit or procedure shown in the SoA in the trial globally.
2. Completion of data analysis
3. Completion of final study report

5 STUDY POPULATION

The study will include 56 participants, randomized in a 3:1 ratio to receive oral sirolimus or matching placebo. All participants will fulfill the diagnostic criteria for probable MSA outlined by the MSA Consensus Criteria (1). Participants with MSA-P and MSA-C diagnosed less than 4 years ago will be accepted into the study. This is because natural history studies have found that later stage MSA patients have only modest rates of progression while patients with milder symptoms have a more rapid rate of progression over 12 months. We hypothesize that these milder cases also have a greater probability to respond to effective treatment. We aim to study 56 participants 30-80 years of age. Sex will be approximately evenly represented. It is expected that approximately 10% of participants will be from ethnic minorities.

5.1 INCLUSION CRITERIA

1. Participants aged 30-80 years old with a diagnosis of MSA. Patients have to fulfill current consensus criteria (1) for probable MSA of the parkinsonian subtype (MSA-P) or cerebellar subtype (MSA-C).
2. Participants who are less than 4 years from the time of documented MSA diagnosis.
3. Participants who are still able to walk with or without assistance.
4. Participants with an anticipated survival of at least 3 years in the opinion of the investigator.
5. Participants who are willing and able to give informed consent.
6. Montreal Cognitive Assessment (MoCA) > 20.
7. Ability to take oral medication and be willing to adhere to the study drug regimen
8. For females of reproductive potential: agreement to use highly effective contraception method during study participation and for an additional 8 weeks after the end of study drug administration
9. For males of reproductive potential: use of condoms or other methods to ensure effective contraception with partner
10. Agreement to adhere to Lifestyle Considerations (see section 5.3) throughout study duration

5.2 EXCLUSION CRITERIA

1. Women of childbearing potential who do not practice an acceptable method of birth control. Acceptable methods of birth control in this study are: surgical sterilization, intrauterine devices, partner's vasectomy, a double-protection method (condom or diaphragm with spermicide), hormonal contraceptive drug (i.e., oral contraceptive, contraceptive patch, long-acting injectable contraceptive) with a required second mode of contraception.
2. Participants with a clinically significant or unstable medical or surgical condition that, in the opinion of the investigator, might preclude safe completion of the study or might affect the results of the study. These include severe uncontrolled congestive heart failure, recent (<6 months) myocardial infarct, severe uncontrolled cardiopulmonary disease, severe, uncontrolled hypertension (sustained systolic blood pressure above 200 mmHg in any position), thrombocytopenia (< 50 x 10⁹/L), severe anemia (< 8g/dl), immunocompromised state, liver or kidney disease (creatinine > 1.5 mg/dl or proteinuria > 20 mg/dl), uncontrolled diabetes mellitus (HbA1c >10g%), alcoholism, amyloidosis, uncontrolled hypothyroidism, sympathectomy, unstable peripheral neuropathies, concurrent infections, severe orthopedic problems that compromise mobility and activity of daily living, recent (< 6 months) cerebrovascular accidents, neurotoxin or neuroactive drug exposure, parkinsonism due to drugs (including neuroleptics, alpha-methyl dopa, reserpine, metoclopramide).
3. Participants with high LDL cholesterol levels (LDL > 190 mg/dL) and/or high triglycerides levels (> 500 mg/dL) under fasting conditions. Patients receiving medications for elevated cholesterol or triglycerides are eligible to participate as long as their LDL cholesterol and/or triglyceride levels are below the abovementioned limits.
4. Participants with positive interferon-gamma release-assay (QUANTIFERON®) indicating latent tuberculosis infection. Participants with a positive Quantiferon® may be enrolled after the patient has been evaluated by an infectious diseases specialist that has cleared the patient for this trial.

5. Participants with history of untreated tuberculosis. Participants with a history of treated tuberculosis may be enrolled after an infectious diseases specialist evaluates patient and has cleared the patient for this trial.
6. Participants with a history of active, acute or chronic, or latent hepatitis B or hepatitis C.
7. Participants with human immunodeficiency virus (HIV) infection, or other congenital or acquired causes of immunosuppression.
8. Participants with a nasal swab PCR positive for COVID-19. If positive, participant may be re-screened after 1 month. If the second nasal swab PCR is negative for COVID-19, participant may be enrolled.
9. Participants with active malignant neoplasms or history of malignant neoplasm in the last 5 years.
10. Movement disorders other than MSA; e.g., Parkinson disease, dementia with Lewy bodies, essential tremor, progressive supranuclear palsy, spinocerebellar ataxia, spastic paraparesis, corticobasal degeneration, or vascular, pharmacological or post-encephalitic parkinsonism.
11. Dementia (DSM-V criteria).
12. History of electroconvulsive therapy.
13. History of deep brain stimulation surgery.
14. Patients with contraindication for MRI scanning, including those with MRI-incompatible pacemaker
15. History of organ transplant
16. Participants who have taken any investigational products within 60 days prior to baseline.
17. Treatment with cyclosporine, oral or intravenous corticosteroids, methotrexate, rituximab within 3 months prior to baseline.
18. Treatment with inhibitors of CYP3A4 (which may decrease the metabolism of sirolimus and increase sirolimus levels): nifedipine, verapamil, clotrimazole, fluconazole, itraconazole, clarithromycin, erythromycin, troleandomycin, cisapride, metoclopramide, bromocriptine, cimetidine, danazol, HIV-protease inhibitors (e.g., ritonavir, indinavir); grapefruit.
19. Treatment with inducers of CYP3A4 (which may increase the metabolism of sirolimus and decrease sirolimus levels): carbamazepine, phenobarbital, phenytoin, rifabutin, rifapentine.
20. Inability or unwillingness of subject to give written informed consent.

5.3 LIFESTYLE CONSIDERATIONS

During this study, participants are asked to:

- Refrain from consumption of red wine, Seville oranges, grapefruit or grapefruit juice from 30 days before the start of study drug until after the final dose.
- Participants who use tobacco products will be instructed that use of nicotine-containing products (including nicotine patches) will not be permitted while they are in the clinical unit.
- Minimize interactions with household contacts that may be immunocompromised.

5.4 SCREEN FAILURES

Screen failures are defined as participants who consent to participate in the clinical trial but are not subsequently randomly assigned to the study intervention or entered in the study. A minimal set of screen failure information is required to ensure transparent reporting of screen failure participants, to meet the Consolidated Standards of Reporting Trials (CONSORT) publishing requirements and to

respond to queries from regulatory authorities. Minimal information includes demography, screen failure details, eligibility criteria, and any serious adverse event (SAE).

A screen failure log will be maintained in the study binders.

Individuals who do not meet the criteria for participation in this trial (screen failure) because of an unallowable medication may be rescreened after discontinuation of such medication. Individuals who do not meet the criteria for participation in this trial (screen failure) because of an acute infection may be rescreened after resolution of such infection. Rescreened participants should be assigned the same participant number as for the initial screening.

Individuals with a positive Quantiferon® will be recommended to see an infectious diseases specialist. In the event that the infectious diseases specialist considers that the positive Quantiferon® was a false positive, or that there is negligible safety risks for a patient with positive Quantiferon® to be enrolled in the study, the patient will be re-screened.

5.5 STRATEGIES FOR RECRUITMENT AND RETENTION

Patients with MSA will be recruited from those that we are currently following at the NYU Dysautonomia Center. Our Center currently follows approximately 100 patients with MSA. In addition, we are in close contact with MSA patients advocacy groups (e.g. *Multiple System Atrophy Coalition*) and will collaborate closely with them in order to disseminate information about the trial and increase the likelihood of recruitment, by means of e-mail blast or letter. The recruitment e-mail/letter to be sent to patients with MSA is attached as an appendix. Any recruitment e-mail or letter to be used in this trial will be submitted to the IRB for approval prior to use.

We expect to screen an average of 8 patients per month and accruing an average of 3 patients per month. At this predicted rate, we expect to complete enrollment of the subjects (n=56) within 24 months with patients recruited only at the NYU Dysautonomia Center. A special effort will be made to include women and minorities.

A screening and enrollment log to record the consent and screening of all subjects and the outcome of each screening will be maintained. The log will provide a comprehensive list of all subjects who were screened for eligibility as well as consented, including the screened failures, the reasons for ineligibility, and reasons for nonparticipation of eligible subjects. This information will be collected centrally, will be included in the Essential Documents Binder, and will be used to enhance subject recruitment efforts.

The principal investigators or co-investigators will approach patients with MSA during a routine clinic visit to inquire whether they would be interested in being enrolled in this clinical trial. If so, patients will be given the consent form. The subject and family will be given enough time to read the informed consent in a quiet room to maintain privacy. The principal investigators, co-investigator or clinical study manager will explain the design of the study, discuss it with the patient and answer any questions or concerns. If the patient is satisfied by the responses of the investigators, the principal investigator will ask the patient to sign the consent form before entering the study. The original signed form will be kept within the study files, and the patient and family will be given a copy.

Screening procedures will include demography, medical history, inclusion and exclusion criteria

assessment, disease diagnosis confirmation, physical examination, vital signs & height/weight, EKG, concomitant medication, adverse events, laboratory testing (serum pregnancy test, if applicable, CBC, metabolic panel, CPK, urinalysis and 24-hour urine collection, QuantiFERON®, hepatitis B and C and HIV testing), and UMSARS scale. There will be a screening period of up to 42 days.

To encourage retention, participants will be compensated for the time/travel/meals with \$75 per visit. This will be done with a check payable to the subject, mailed to the subject's mail address within 30 days after the study visit.

5.5.1 USE OF DATACORE/EPIC INFORMATION FOR RECRUITMENT PURPOSES

This study will utilize EPIC to identify participants.

Any recruitment information sent by email will utilize Send Safe email.

Once potential participants have been identified, the study team will notify the treating physician (TP) that they have patients eligible to participate as follow:

- TP agrees to permit study team to directly contact potential participants on behalf of TP.
- TP has been notified that the study team will contact potential participants directly, phone, email, and/or the MyChart portal.

Once contact is made, approved recruitment language will be used to communicate the reason they are being contacted and participants will be asked if they are interested in participating in this specific study. Should the potential participants agree, the study team will provide the participants with information regarding the next steps for participation.

If a participant requests information regarding opting out of further recruitment for all research, participants will be directed to contact [contact] or [name].

6 STUDY INTERVENTION

6.1 STUDY INTERVENTION ADMINISTRATION

6.1.1 STUDY INTERVENTION DESCRIPTION

Sirolimus (a.k.a. rapamycin, a.k.a. Rapamune) is an immunosuppressive agent. Sirolimus is a macrocyclic lactone produced by *Streptomyces hygroscopicus*. The chemical name of sirolimus (also known as rapamycin) is (3*S*,6*R*,7*E*,9*R*,10*R*,12*R*,14*S*,15*E*,17*E*,19*E*,21*S*,23*S*,26*R*,27*R*,34*aS*)-9,10,12,13,14,21,22,23,24,25,26,27,32,33,34,34*a*-hexadecahydro-9,27-dihydroxy-3-[(1*R*)-2-[(1*S*,3*R*,4*R*)-4-hydroxy-3-methoxycyclohexyl]-1-methylethyl]-10,21-dimethoxy-6,8,12,14,20,26-hexamethyl-23,27-epoxy-3*H*-pyrido[2,1-*c*][1,4]oxaazacyclohentacontine-1,5,11,28,29 (4*H*,6*H*,31*H*)-pentone.

Its molecular formula is $C_{51}H_{79}NO_{13}$ and its molecular weight is 914.2. Sirolimus is a white to off-white powder and is insoluble in water, but freely soluble in benzyl alcohol, chloroform, acetone, and acetonitrile.

Sirolimus is available for administration as an oral solution containing 1 mg/mL sirolimus. Sirolimus is also available as a tan, triangular-shaped tablet containing 0.5 mg sirolimus, as a white, triangular-shaped tablet containing 1 mg sirolimus, and as a yellow-to-beige triangular-shaped tablet containing 2 mg sirolimus. The inactive ingredients in sirolimus tablets include sucrose, lactose, polyethylene glycol 8000, calcium sulfate, microcrystalline cellulose, pharmaceutical glaze, talc, titanium dioxide, magnesium stearate, povidone, poloxamer 188, polyethylene glycol 20,000, glyceryl monooleate, carnauba wax, dl-alpha tocopherol, and other ingredients. The 0.5 mg and 2 mg dosage strengths also contain yellow iron (ferric) oxide and brown iron (ferric) oxide.

In this trial, sirolimus capsules (2 mg) and matching placebo will be manufactured in compliance with current GMP standards and guidelines applicable to study drugs. Sirolimus capsules (2 mg) and their matching placebo will be of identical appearance to maintain study blinding.

This trial will use sirolimus (Rapamune®) 2 mg tablets manufactured by *Pfizer* (NDC #: 0008-1032-05). Matching placebo will be compounded by [name], Town Total Compounding Center.

The matching placebo will be composed of lactose and encapsulated in an orange gelatin capsule.

6.1.2 DOSING AND ADMINISTRATION

During the baseline visit, participants will be allocated to a treatment group, based on a randomization procedure employing a 3:1 assignment ratio, and a scheme using blocks stratified by MSA type (cerebellar or parkinsonian) and sex. The randomization sequence will be performed by the independent medical monitor (IMM) and delivered, in a closed envelope, to Town Total Compounding Pharmacy ([name]). The Town Total Compounding Pharmacy pharmacist will use the randomization order to send the proper medication to the study coordinator. The patient will be then instructed to take one capsule (i.e., 2 mg of sirolimus or matching placebo) daily and have sirolimus levels in blood 7 days (with a window of 3 days after the target date) after start of study drug.

Participants will then undergo a dose-selecting procedure based on therapeutic level measurements. The results of these measurements will be revealed only to an independent study pharmacist (independent from the Town Total Compounding pharmacy) who will make dosing recommendations to maintain sirolimus trough levels between 5 and 20 ng per milliliter, as well as corresponding sham dose adjustments in the placebo group.

Until the dose selection period has been completed, subjects will undergo sirolimus measurements in blood frequently during the first month of study drug treatment. Sirolimus levels will be measured again 7 days (with a window of 3 days after the target date) after a subject has been instructed to increase the dose of study drug. Once the initial dose selection has been achieved, subjects will then undergo measurements of sirolimus in blood levels monthly since the start of the study drug (with a window of 15 days after the target date).

The initial dose selection period is as follows: from day 1 to day 7, all subjects will receive sirolimus 2 mg one capsule daily or matching placebo. Seven days later (+ 3 days), subjects will undergo measurement of sirolimus levels. Once the results of the levels are back, the independent pharmacist will assess and determine if an increase in study drug is required.

- If sirolimus levels are < 5 ng/mL, the participant will be instructed to take sirolimus 2 mg two capsules daily (4 mg total dose) or matching placebo; sirolimus levels will be then measured again 7 days after the patient began taking 4 mg/day (+ 3 days). If sirolimus levels are between 5 and 20 ng/ml, the subject will continue with that dose until the next measurement of sirolimus levels on Visit (+ 3 days).
- If sirolimus levels are > 30 ng/ml with one capsule/day, the subject will be excluded from the trial due to the high risk of adverse events.

Subjects who were instructed to increase their dose to 4 mg will undergo another measurement of sirolimus levels 7 days after the previous dose adjustment (+ 3 days):

- If sirolimus levels are < 5 ng/mL, the participant will be instructed to increase sirolimus to 2 mg three capsules daily (6 mg total dose) or matching placebo. Sirolimus levels will be then measured 7 days after the patient began taking 6 mg/day (+ 3 days).
- If sirolimus levels are between 5 and 20 ng/ml, the subject will continue with that dose until the next measurement of sirolimus. If the sirolimus levels are > 20 ng/ml, the subject will be instructed to go back to the 2 mg/day dose and continue with that dose until the next measurement of sirolimus levels.

From Visit 3 to Visit 6, sirolimus level blood draw will take place 7 days (+3 days) after the previous dose adjustment has taken place (i.e., 7 days after the patient started taking the adjusted dose).

From Visit 7 onwards, subjects will be instructed to increase or decrease their sirolimus dose (between a min dose of 2 mg/day to a max dose of 6 mg/day) depending on blood levels (target: 5-20 ng/ml) and the emergence of adverse events.

Expected dose-limiting effects requiring sirolimus dose reduction are:

- Grade 2 stomatitis or mucositis
- Grade 2 lymphedema
- Grade 2 proteinuria
- Grade 2 renal failure
- Grade 3 pneumonitis
- Grade 2 diarrhea

Every attempt will be made to maintain the participant on the full dose. If the participant is unable to maintain the full dose, the minimum acceptable dose is 2 mg once a day. An attempt will be made to increase the dose with a re-challenge at a later date. Capsules should be swallowed whole with a glass of water or may be taken with food to minimize gastrointestinal side effects.

To maintain investigator and subject blinding during the clinical trial, the results of the sirolimus

measurements in blood will be revealed only to an independent study pharmacist who will make dosing recommendations, and a sham therapeutic drug level will be simulated for those patients receiving placebo (66) (see **Measures to Minimize Bias** section).

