--	--

Phase:	Phase II
Description of Sites:	Single-center clinical trial performed at the New York University Langone Medical Center
Description of Study Intervention:	Oral sirolimus capsules at a dosage of 2 mg (one 2 mg capsule), 4 mg (two 2 mg capsules) or 6 mg (three 2 mg capsules) taken once a day. Dosage will be adjusted based on determination of sirolimus levels in blood performed throughout the trial and on the frequency of adverse events related to the study drug.
Study Duration:	3 years
Participant Duration:	48 weeks plus a safety follow-up phone call 2 weeks after the end of the trial.

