- CBC, CMP, CPK (8 ml of blood) and urinalysis with 24-hour urine collection
- Lipid panel (2 ml of blood)
- Sirolimus levels in blood (5 ml of blood)
- Adverse event reporting

In case the safety lab assessments are performed locally (e.g., at a local laboratory near the subjects' home), the PI or a licensed research member of the team will provide the patient with a prescription for the required tests. A research nurse, investigator or study manager will perform a phone call to assess adverse events within 7 days of the study visit.

To account for delays during the first month of treatment, Visit 7 (2-month) may be skipped to ensure that Visit 8 occurs 3 months (+/- 15 days) after the initiation of the study drug.

To maintain the blinding, the results of the sirolimus levels in blood will remain blinded to the investigators and study coordinators and delivered to the independent pharmacist in charge of determining if the sirolimus dosage should be increased or decreased.

End of study visit/early termination: the following tasks/procedures will be performed at the clinic during the termination visit (Study Visit 17):

- EKG
- MoCA
- Concomitant medications
- Physical examination
- Vitals signs
- CBC, CMP, CPK (8 ml of blood) and urinalysis with 24-hour urine collection
- Lipid panel (2 ml of blood)
- Sirolimus levels in blood (5 ml of blood)
- Retrieve study medication
- Recording of AE
- UMSARS scale
- Blood sample for exosomes (2 ml of blood)
- Retinal optical coherence tomography
- Brain MRI

We will accept a visit window of 15 days before or after the target date of this visit.

The reason for discontinuation of therapy will be documented in the source documents and captured on the CRF. In the event that the study drug is discontinued early, an early termination visit should be

completed as close to the last dose date as possible. Participants will be followed for the duration of 12 months.

If a participant is withdrawn because of an adverse event, the appropriate “Withdrawal Section” of the CRFs should be fully completed in addition to the Adverse Event module. The Independent Medical Monitor should be informed of all participants who are withdrawn for this reason. Participants will be followed for 12 months.

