7.2 PARTICIPANT DISCONTINUATION/WITHDRAWAL FROM THE STUDY

Participants are free to withdraw from participation in the study at any time upon request. An investigator may discontinue or withdraw a participant from the study for the following reasons:

- Pregnancy
- Significant study intervention non-compliance
- If any clinical adverse event (AE), laboratory abnormality, or other medical condition or situation occurs such that continued participation in the study would not be in the best interest of the participant
- Disease progression which, in the opinion of the investigator, requires discontinuation of the study intervention
- If the participant meets an exclusion criterion (either newly developed or not previously recognized) that precludes further study participation
- Participant unable to receive study drug for 15 days or more.

The reason for participant discontinuation or withdrawal from the study will be recorded on the electronic Case Report Form (CRF). Subjects who sign the informed consent form and are randomized but do not receive the study intervention may be replaced. Subjects who sign the informed consent form, and are randomized and receive the study intervention, and subsequently withdraw, or are withdrawn or discontinued from the study, will not be replaced.

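### At 2 mg/day the dose reduction that section 6.1.2 requires conflicts with its own dose floor, and blood levels above 20 and up to 30 ng/ml have no stated action

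*Combined protocol and SAP*

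**What the plan says.** **Dose steps and start.** The synopsis (1.1) builds every dose from one unit: "Oral sirolimus capsules at a dosage of 2 mg (one 2 mg capsule), 4 mg (two 2 mg capsules) or 6 mg" (three capsules). Section 6.1.2 starts everyone on the lowest step: "from day 1 to day 7, all subjects will receive sirolimus 2 mg one capsule daily or matching placebo".

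**Adverse events.** Section 6.1.2 introduces a list with the words "Expected dose-limiting effects requiring sirolimus dose reduction are". Six entries follow: stomatitis or mucositis, lymphedema, proteinuria, renal failure and diarrhea, each at Grade 2, and pneumonitis at Grade 3. The next paragraph asks staff to try to hold the full dose and to re-challenge later, and sets the floor: "If the participant is unable to maintain the full dose, the minimum acceptable dose is 2 mg once a day".

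**Blood levels in dose selection.** The target trough is 5-20 ng/ml. At 2 mg/day, a level below 5 leads to 4 mg/day and a level of 5-20 leads to no change. At the top, "If sirolimus levels are > 30 ng/ml with one capsule/day, the subject will be excluded from the trial". At 4 mg/day, a level below 5 leads to 6 mg/day, 5-20 to no change, and above 20 to a return to 2 mg/day.

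**From Visit 7.** Doses go up or down "between a min dose of 2 mg/day to a max dose of 6 mg/day) depending on blood levels (target: 5-20 ng/ml) and the emergence of" toxicity.

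**Who sees what, and who decides.** Section 4.1 states that "the results of the sirolimus levels in blood will remain blinded to the investigators and study coordinators"; an independent pharmacist receives them. Section 7.1 leaves any change in management after a clinically significant finding to the investigator or a designee. Section 7.2 begins "An investigator may discontinue or withdraw a participant from the study for the following reasons", and its reasons include adverse events and laboratory abnormalities.

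**The concern.** A safety rule that calls for a reduction has to be executable at the dose the participant is taking. At 2 mg/day the reduction list and the floor, a few lines apart in the same section, cannot both be followed. The level rules add a separate problem: a result above the plan's own target can come back at 2 mg/day with nothing written to say what follows.

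The drug is an immunosuppressant, and 6.1.2 itself gives adverse-event risk as the reason for the exclusion above 30 ng/ml. If the response to an above-target level is not written down, it has to be improvised for each participant. Similar participants may then be handled differently. No matching sham action is defined for placebo either, so an ad hoc change could hint at allocation. Stopping because of adverse events is the primary safety outcome in 8.2, so uneven handling would also feed into a reported result.

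**Working it through.** The plan states no figure to reproduce. The check sets each dose step against each rule.

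**Step 1: lower doses available.** The permitted doses are 2, 4 and 6 mg/day (1.1, 6.1.2).
- Below 6 mg/day: 4 and 2.
- Below 4 mg/day: 2.
- Below 2 mg/day: none.

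**Step 2: the reduction list.** At 4 or 6 mg/day a reduction can be carried out for all six listed events. At 2 mg/day it can be carried out for 0 of 6. This affects everyone in week 1, anyone in range at the first level check, and anyone sent back from 4 mg/day.

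**Step 3: explicit level rules during dose selection (6.1.2).**

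| Current dose | < 5 ng/ml | 5-20 | > 20 to 30 | > 30 |
|---|---|---|---|---|
| 2 mg/day | to 4 mg/day | continue | none stated | excluded |
| 4 mg/day | to 6 mg/day | continue | back to 2 mg/day | back to 2 mg/day |
| 6 mg/day | no bullet | no bullet | no bullet | no bullet |

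Three of four bands are covered at 2 mg/day and four of four at 4 mg/day. At 6 mg/day a level is ordered but no bullet follows. There the general instruction to the pharmacist, to keep troughs within 5-20, still applies, and two lower steps exist for a high level. That general instruction does not rescue 2 mg/day, because no lower step exists to recommend. A participant returned from 4 to 2 mg/day whose level stays above 20 and up to 30 lands in the same empty cell.

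**Step 4: Visit 7 onward.** Changes stay within 2-6 mg/day. At 2 mg/day, both bands above 20 therefore have no dose decrease. The exclusion above 30 ng/ml stands among the dose-selection bullets, and the Visit 7 rule does not say whether it continues.

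**Step 5: other routes.** Sections 7.1 and 7.2 act on the investigator's judgement. All six listed events are clinical or routine-laboratory findings, so a blinded investigator can see them and use those routes. A blood level is different. The investigator does not see it, and the pharmacist who does has no written instruction for above 20 and up to 30 ng/ml at 2 mg/day. Section 6.1.2 does not refer to 7.1 or 7.2 for either case.

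**The case against.** The strongest reply is that the plan has other ways to act. Section 7.1 allows a change in management and treats stopping the drug as separate from leaving the study. Section 7.2 permits withdrawal for toxicity, and its limit of 15 days off drug presupposes shorter interruptions. Section 4.1 provides an early-termination visit. The exclusion above 30 ng/ml already starts from a result that the pharmacist holds. Section 10.1.6 puts the pharmacist and the medical monitor, both unblinded under 6.3, on monthly safety calls. A floor can also be read as meaning that someone who cannot tolerate 2 mg/day comes off study drug.

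Much of this stands, and it rules out several stronger readings that a reader might infer:
- **That toxicity found by monitoring leads nowhere.** It does not: discretionary routes exist at any dose for all six listed events.
- **That whoever knows the level cannot act.** The exclusion rule and the monthly calls contradict this.
- **That 6 mg/day is unregulated in dose selection.** The general target rule covers it.
- **That an above-target participant waits up to 28 + 15 = 43 days for another level.** This is not a firm figure. Section 4.1 allows unscheduled visits with a level, and the visit windows are worded differently in 1.3 and 4.1.

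Two things remain. A discretionary option does not replace an action that 6.1.2 words as required, and the reading that 2 mg/day intolerance means stopping is nowhere written. For the level gap, the calls are a weak substitute: the information that 10.1.6 has the investigator bring covers recruitment, screen failures, withdrawals and adverse events, not levels, and the blinded investigator is on the call.

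**Conclusion.** The point holds as a contradiction between stated safety rules, together with a gap in the level rules. It is confined to 2 mg/day: the required reduction is not executable for six of six listed events, one of four level bands has no action in dose selection, and no decrease is available for either band above 20 ng/ml from Visit 7. It is more than missing detail, because the investigator cannot see the level gap and the pharmacist has no instruction for it.

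The size is a count of rules, not of participants. The documents do not say how often 2 mg/day gives a level above 20 ng/ml, nor how many participants stay on that dose. The conclusion assumes that 6.1.2 is the full dosing instruction; a separate pharmacist's manual could contain more, but the protocol does not cite one for this purpose.

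**What to change.** Reconcile four elements of 6.1.2 with each other and with 7.1 and 7.2: the dose-reduction list, the 2 mg/day minimum, the 5-20 ng/ml target and the rule above 30 ng/ml. Afterwards every level band and every listed event at 2 mg/day should have a stated action that can be carried out, both in dose selection and from Visit 7. The text should say whether the rule above 30 ng/ml continues after dose selection, refer to 7.1 and 7.2 where those are meant to apply, and keep the blind, including matching sham handling for placebo.

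The clinical content is for the sponsor and the medical monitor; no dose or clinical rule is proposed here. Layout, and who starts each action, are also theirs to settle.

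The cost is a protocol amendment and matching written instructions for the independent pharmacist. The reconciliation needs no new data collection in itself; whether the chosen actions add tests or visits depends on their content.
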